- review of medication list daily
- review of toxicity/adverse events daily
- vital signs (pre- and post-infusion of BMS-986253) and three times per day including temperature, heart rate, blood pressure, respiratory rate, oxygen saturation and FIO₂ and SpO₂/FIO₂ if on supplementation oxygen.
- physical exam daily
- hematological laboratories (hemoglobin, hematocrit, white blood cell count with differential [including absolute eosinophil count], platelets) daily
- coagulation profile (INR, aPTT) as clinically indicated.
- serum chemistry profile (sodium, potassium, chloride, bicarbonate, urea, creatinine, glucose, calcium, albumin, total protein, bilirubin, ALT, AST, alkaline phosphatase) daily
- CRP, D-Dimer, LDH, sIL-6 level every other day
- Neutrophil-to-lymphocyte ratio (NLR), absolute lymphocyte count daily
- NEWS2 score daily
- 7-point ordinal score daily
- CT or CXR of the chest weekly (+/- 2 days) (optional)
- Sera for biomarker and PK analysis day 8, 15, 22, 29, and EOT (+/- 2 days). Where possible, the Day 15 and 29 PK samples should be collected just prior to dosing (optional). For patients ready for discharge prior to day 8, a serum sample should be collected, when feasible, prior to discharge.
- Patients randomized to anti-IL-8 therapy will receive BMS-986253 every 2 weeks (+/- 2 days) x 1-3 doses, with 2nd dose given if patient still hospitalized and then 3rd dose optional if patient still hospitalized with severe COVID-19. Patients randomized to control will receive standard of care.

10.3 Follow-Up After Discharge:

Following completion of therapy, patient will have follow up by phone every 30 days for the first 100 days following the last dose of therapy. Patients will then have follow up by phone every 90 days (+/- 30 days) for up to 1 year. In addition, patients will be assessed 28 days (+/- 2 days) following start of treatment whether they are discharged or in the hospital. These assessments will include:

- review of medication list
- review of toxicity/adverse events (for up to 100 days following last dose of treatment)
- Evaluation of Katz basic ADLs and Lawton IADLs (Appendix C and D)

- assessment for survival

Patients withdrawing from the study early because of adverse events should be followed until the adverse event has either resolved or stabilized. Reasons for premature withdrawal should be determined and documented.

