11. MEASUREMENT OF EFFECT

11.1 Primary Endpoint

11.1.1 *Time to improvement (2 points) in 7-point ordinal scale*

The time to improvement (2 points) will be defined as the time (days) required from the start of treatment to the improvement of clinical status (2 points) assessment from baseline based on the 7-point ordinal scale. Patients for whom there was no event will be censored from this analysis. 7-point ordinal scale will be calculated as follows: (1) death, (2) hospitalized on invasive mechanical ventilation or extracorporeal membrane oxygenation, (3) hospitalized, requiring non-invasive ventilation or high flow nasal cannula, (4) hospitalized, requiring supplemental oxygenation (5) hospitalized, not requiring supplemental oxygenation and requiring ongoing medical care (COVID-19 related or otherwise) (6) Hospitalized, not requiring supplemental oxygen – no longer requires ongoing medical care, (7) not hospitalized.

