11.2 Secondary Endpoints

11.2.1 *Time to death*

The time to death will be defined as the time from onset from symptoms until death from any cause. Patients who are alive or lost to follow-up at the cut-off date will be censored from this analysis.

11.2.2 *Mortality at 1 month*

1-month mortality is defined as the percentage of patients who have died 1 month from the time of start of treatment.

11.2.3 *Time to intubation*

The time to intubation will be defined as the time from symptom onset until time of intubation. Any patients already intubated at enrollment will be censored from this analysis.

11.2.4 *Time to improvement in oxygenation*

The time to improvement in gas exchange will be defined as the time from time of start of treatment until a $\geq 30\%$ decrease in oxygen requirement compared to

baseline [or elimination of oxygen requirement] without a decrease in SpO2 sustained for at least 48hrs or until discharge.

11.2.4 *Proportion of patients requiring ICU admission at 1 month.*

The proportion of patients requiring ICU admission will be calculated as the number of patients requiring ICU admission over the course of their hospitalization over the number of evaluable patients.

11.2.5 *Safety and Toxicity*

All subjects receiving at least one dose of the study drug will be evaluated for safety by monitoring symptoms, physical examinations, and laboratory tests. Adverse events will be classified and graded according to the NCI Common Toxicity Criteria version 5.0 (see Appendix A). The absolute number and frequency of each adverse event will be reported, and subdivided according to toxicity grade. A description of adverse events by treatment arm will also be reported. A particular adverse event occurring more than once in the same subject will be counted only once and at its worse grade.

11.2.6 *Duration of Hospitalization*

Duration of hospital admission will be measured from the time of admission until the time of discharge.

11.2.7 *7-point Ordinal Scale Score*

The mean/medians of the 7-point ordinal raw scores at day 14 from the start of treatment will be computed and compared between the treatment and control groups.

Exploratory Endpoints.

11.2.8 *Change in inflammatory markers from baseline*

Changes in LDH, D-Dimer, CRP, ESR, NLR and absolute lymphocytes before and after treatment and over time will be measured every other day during hospitalization.

11.2.9 *Change in circulating sIL-6 levels from baseline*

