11.2.13 To measure time on ventilation

Measured from time of intubation to time of definitive extubation. Will censor for patients not requiring intubation.

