13 STATISTICAL CONSIDERATIONS

13.1 Study Design and Sample Size

This study is a single-center, randomized open-label phase 2 trial to evaluate the efficacy and safety of anti-IL-8 in hospitalized adults with severe or critical COVID-19. The primary endpoint is time to improvement in clinical status: the time (days) required from the start of treatment to the improvement of clinical status (2 points) assessment from baseline based on the 7-point ordinal scale. Patients for whom there was no event will be censored.

Patients will be randomized in a 2:1 allocation ratio to either anti-IL-8 or standard of care. Patients will be assessed daily while hospitalized. Discharged patients will be contacted by telephone on Day 29 and then monthly up to one-year to assess status. In addition to these specific assessment times, one interim analysis is planned at and the DSMC will actively monitor interim data to make recommendations about early signs of overwhelming efficacy and futility/study closure (see Section 13.4.)

With a sample size of 138 patients: N=92 patients randomized to the treatment arm and N=46 patients assigned to the standard of arm/control, the study will have 80% power to detect an increase in median time to improvement from 2 days (control) to 5 days (treatment arm) with one-sided alpha of 0.025. The sample size was estimated based on a hazard ratio (HR) of 0.40 assuming an exponential survival distribution with inflation to account for one interim look and 5% drop-out rate.

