13.2 Study Endpoints and Analysis Plan

All subjects who receive at least one dose of study drug will be considered evaluable and included in the efficacy and safety analysis.

Analytic plan for primary objective:

The primary efficacy null hypothesis of the equality of time to improvement (2 points) in clinical status curves will be tested with the log-rank test. The overall type I error for the primary analysis will be considered one-sided alpha of 0.025. Kaplan-Meier estimates will be reported for each of the two arms with median time to improvement and 95% confidence intervals (CI). Cox regression will be employed to estimate the treatment effect (HR) and 95% CI.

Analytic plan for secondary and exploratory objective:

We will estimate the distributions of all time-to-event endpoints using the Kaplan-Meier method and if possible, provide medians (95% CI). Comparisons between survival curves will be assessed using log-rank tests and Cox regression models.

For each arm, we will estimate the 1-month mortality rate and incidence of adverse events graded by CTCAE v5.0 using the exact 95% confidence intervals. Comparisons between the two arms will be assessed using chi-squared or Fisher's exact tests. The mean/medians of the 7-point ordinal scores at day 14 after the start of treatment will be computed and compared between the two groups using two-sample t-test or the equivalent non-parametric Wilcoxon Rank-Sum test if normality is not satisfied.

Changes in exploratory endpoints (before and after treatment) will be quantified using means (95% CI) and/or medians (inter-quartile ranges) for non-normal data. Comparisons between the two arms will be made using two-sample independent t-tests or the non-parametric equivalent, Wilcoxon Rank-Sum test. The associations between baseline levels and/or changes over time of IL-8 and other key cytokines (TNF, IL-1b, IL-6) with outcomes will be assessed using regression models.

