13.4 Interim analyses

One interim analysis is planned after approximately 17 (40% of the total 41 events) have been observed using O'Brien and Fleming stopping boundary using the Lan-DeMets spending function at a nominal type I error of 0.025. The intent-to-treat (ITT) principle is applied to the analysis, and therefore, we inflated the sample size by 5% to safeguard against drop-outs.

An independent Data Safety Monitoring Committee (DSMC) will serve as the primary reviewer of the results of the interim analyses of the study and will make recommendations for discontinuation of the study or protocol modifications. Stopping rules for overwhelming efficacy and/or futility are provided in Table 4 below.

Table 4. Efficacy and Boundaries and Properties for the Time to Improvement Analysis

Analysis*	Value	Efficacy	Futility
IA1: 40%	Nominal critical point Z-value	3.3569	0.0811
N: 138	p (1-sided)	0.0004	0.4677
Events: 17	~HR at bound	0.1720	0.9584
Month: 2.6	P(Cross) if HR=1	0.0004	0.5323
	P(Cross) if HR=0.4	0.0599	0.0427
IA2: 100%	Nominal critical point Z-value	1.9622	1.9622
N: 138	p (1-sided)	0.0249	0.0249
Events: 41	~HR at bound	0.5217	0.5217
Month: 7	P(Cross) if HR=1	0.0240	0.9760
	P(Cross) if HR=0.4	0.8000	0.2000

*This column displays the number of events and percentage (%) of needed time to improvement events, the expected sample size (N), and the estimated months (Month) after first participant is randomized for each analysis.

p (1-sided): the nominal α for testing.

~HR at bound: the approximate hazard ratio required to reach the bound for overwhelming efficacy or futility stop.

P (Cross if HR=1): the probability of crossing a bound at or before each analysis under the null hypothesis.

P (Cross if HR=0.40): the probability of crossing a bound at or before each analysis under the alternative hypothesis.

Abbreviations: HR = hazard ratio; IA = interim analysis.

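### Deaths are censored with no stated time and no competing-event method, so the planned Kaplan-Meier curves overstate the proportion of patients who improve

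*Combined protocol and SAP*

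**What the plan says.** Section 11.1.1 defines the primary endpoint as days from start of treatment to a 2-point improvement and lists death as category 1 of the scale. Its only handling rule is "Patients for whom there was no event will be censored from this analysis". Section 13.1 repeats it in shorter form: "Patients for whom there was no event will be censored". Neither gives a censoring date, an analysis horizon or a separate provision for death.

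Section 13.2 tests the improvement curves with the log-rank test, estimates the hazard ratio by Cox regression, and adds: "Kaplan-Meier estimates will be reported for each of the two arms with median time to improvement and 95% confidence intervals (CI". For the secondary and exploratory endpoints it says: "We will estimate the distributions of all time-to-event endpoints using the Kaplan-Meier method". No cumulative-incidence or other competing-event method appears in the plan.

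The documents do not use the word censored in one sense only. For time to intubation (11.2.3): "Any patients already intubated at enrollment will be censored from this analysis". For time on ventilation (11.2.13): "Will censor for patients not requiring intubation". Those two uses are closer to exclusion. Section 11.2.1 applies the same phrase as 11.1.1 to patients alive or lost at a cut-off date, which is ordinary censoring.

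A natural horizon already exists. Section 10.3 provides that "patients will be assessed 28 days (+/- 2 days) following start of treatment whether they are discharged or in the hospital".

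**The concern.** A patient who dies before improving can never improve. Kaplan-Meier with censoring at death treats that patient as someone who would have gone on to improve at the same rate as those still at risk. The resulting curve describes a population in which nobody dies, so it lies above the proportion of randomized patients who actually improve. Section 3.1 quotes mortality of about 20-25% in severe disease and section 5.1 also admits critical disease, so deaths before improvement are to be expected.

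At stake is what the trial reports as its main descriptive result: the improvement curve and the median in each arm. Both depend on a censoring time that the plan does not give. The trial is open-label, so that choice should be fixed before outcomes are seen. A second, separate issue is that the primary comparison looks only at the improvement hazard and takes no account of a difference in deaths.

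**Working it through.** **The plan's own figure.** Events for 80% power at hazard ratio 0.40, one-sided 0.025 and 2:1 allocation: (1.960 + 0.842)² / [(2/9)(ln 0.40)²] = 7.85 / 0.1866 = 42.07, rounded up to 43. With 41 events the same formula gives 79.0% power. Table 4's 41 events and 80% are therefore reproduced closely. They concern improvement events and are not in dispute.

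**Inputs.**
- Control median 5 days (Synopsis), taken to be the Kaplan-Meier median with deaths censored at death. Section 13.1 gives the two medians the other way round; the 2-day case is shown below.
- Share p dying before improvement by day 28: 20-25%, with 10-15% as a lower range. This is an assumption, because section 3.1 gives overall mortality in severe disease and not this quantity.
- Horizon 28 days (section 10.3), also an assumption.
- Exponential times.

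**Kaplan-Meier at day 28.** λ = ln 2 / 5 = 0.1386 per day, so 1 − exp(−28λ) = 1 − exp(−3.88) = 97.9%, whatever the death rate.

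**True proportion improved.** Let μ be the death hazard, solved from μ/(λ+μ) × [1 − exp(−28(λ+μ))] = p. The proportion improved by day t is λ/(λ+μ) × [1 − exp(−(λ+μ)t)]. For p = 20%, μ = 0.0350 and λ+μ = 0.1736, so the day-28 value is 0.798 × (1 − 0.008) = 79.2%. The true median is the time at which this function reaches 50%.

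| p | μ per day | Kaplan-Meier, day 28 | True, day 28 | True median (Kaplan-Meier 5.0) |
|---|---|---|---|---|
| 10% | 0.0156 | 97.9% | 88.7% | 5.27 days |
| 15% | 0.0248 | 97.9% | 84.0% | 5.45 days |
| 20% | 0.0350 | 97.9% | 79.2% | 5.67 days |
| 25% | 0.0466 | 97.9% | 74.4% | 5.95 days |

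With a 2-day median and p = 20-25%, Kaplan-Meier reads 100% at day 28 against a true 80-75%, and the true median is 2.3-2.4 days.

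**Timing of deaths.** Keep p = 20-25% and the 5-day median, but let deaths begin only at day s. For t > s the proportion improved is 1 − exp(−λs) + exp(−λs) × λ/(λ+μ) × [1 − exp(−(λ+μ)(t−s))], with μ solved again.
- s = 2: true median 5.3-5.4 days
- s = 3: 5.1-5.2 days
- s = 5: exactly 5.0 days, because half have improved before any death

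The true day-28 figure stays at 75-80% in all three cases. The late part of the curve is therefore biased whatever the timing, while the median may not be.

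**If deaths are instead kept at risk to day 28.** With no other losses, Kaplan-Meier at day 28 is simply the number improved divided by the number randomized, and the bias disappears. The unstated censoring time decides the result.

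**Direction between arms.** Take medians of 5 and 2 days and the same death hazard in both arms. Kaplan-Meier reads 98% v 100% at day 28. The truth is 79% v 91% (p = 20% in controls) or 74% v 88% (25%). In this case the curves understate the drug's advantage.

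**The test.** Simulation with 92 v 46 patients, 10,000 runs per scenario, death hazard doubled on treatment and improvement hazard unchanged. Truly 66% v 79% improve (p = 20%) or 60% v 74% (25%).
- Deaths censored at death: the log-rank rejects for benefit in 1.8% of runs and for harm in 3.2-3.5%.
- Deaths kept at risk to at most 28 days: it rejects for harm in 24-29% at full follow-up (19-24% if same-day ties count as improvement) and in 11-15% at a 41-event cut.
- At the 17-event look with deaths censored at death, Z exceeds 3.3569 in at most 0.05% of runs, in line with Table 4's 0.0004.

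**The case against.** The plan is not silent on death. Death is category 1, so the generic rule already places patients who die unimproved among the censored. What is missing is the censoring time and a competing-event summary. This is right.

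A reader might infer from 11.2.3 and 11.2.13 that patients who never improve are to be dropped altogether. The documents do not support that: 11.2.1 uses the same phrase for ordinary censoring, 13.1 leaves out the last three words, and 13.2 plans methods that handle censored times. One clarifying sentence is enough.

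The inputs are soft. Section 3.1 gives overall mortality, deaths after improvement do not count here, and section 5.2 excludes multi-organ failure requiring vasopressors, hemofiltration or ECMO. Critical disease is eligible, however, so the true share could lie on either side. The constant death hazard puts many deaths early, and with later deaths the median bias shrinks to nothing. This stands, and it is why the median shift is given as a range from zero. It does not remove the day-28 gap.

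Finally, an improvement endpoint is not designed to detect deaths. Time to death and 1-month mortality are compared between arms, and the day-14 score counts death as its lowest category. This also stands: excess mortality would not be hidden from the trial's results.

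**Conclusion.** The point holds as a defect in the planned estimator and its specification. On the ordinary reading, the Kaplan-Meier curves overstate the proportion improved at day 28 by about 19 to 24 points at 20-25% deaths before improvement (97.9 − 79.2 = 18.7; 97.9 − 74.4 = 23.5), and by about 9 to 14 points at 10-15%. The median is understated by 0 to about 1 day. The sizes rest on exponential times, the 5-day median, a 28-day horizon and the assumed share of deaths. The direction of the curve bias does not: it follows whenever deaths precede later improvements.

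A reader might go further and infer that the primary test is invalid, that the interim efficacy stop is too easily reached, or that the bias favours the drug. None of these is supported. The log-rank and Cox analyses validly compare cause-specific improvement hazards, the interim crossing rate agrees with Table 4, and with equal death hazards the curve bias worked against the drug. A false finding of benefit would need the extra deaths to fall on patients unlikely to improve, and nothing in the documents establishes that. What remains for the test is narrower: a drug that raised mortality and left the improvement hazard unchanged would look neutral on it.

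**What to change.** In 11.1.1 and 13.1:
- state one common horizon, for example the existing assessment 28 days after start;
- censor patients alive and unimproved at that horizon, and losses at their last assessment;
- name death without improvement as a competing event;
- state that no patient is excluded for lack of the event.

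In 13.2:
- replace the Kaplan-Meier improvement curves and medians with the cumulative incidence of improvement and the time at which it reaches 50%, shown beside the cumulative incidence of death;
- keep the log-rank and Cox as the primary analyses, described as cause-specific;
- pre-specify one sensitivity comparison in which deaths stay at risk to the horizon (Gray's test or a subdistribution hazard ratio).

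Cost: reported improvement becomes less favourable, and there is a little more analysis in standard software. The score is recorded daily in hospital, discharge is category 7, and survival is assessed 28 days after start, so no new data are needed. Because the primary test does not change, the event target and power are untouched. A 28-day horizon drops later improvements, but at the 5-day median with 20% deaths fewer than 1% of patients would still be alive and unimproved then (exp(−28 × 0.1736) = 0.8%).

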2. STUDY OBJECTIVES

Primary Objective

- To determine the **time to improvement in the 7-point ordinal scale** in patients treated with anti-IL-8 therapy compared to standard of care/controls.
 - Measured from baseline to 2 point or greater improvement in 7-point ordinal scale.

Secondary Objectives

- To evaluate the **time to death** in patients treated with anti-IL-8 therapy compared to controls.
- To evaluate the **mortality 1 month** after start of treatment in patients treated with anti-IL-8 therapy compared to controls.
- To determine the **time to intubation** in patients treated with anti-IL-8 therapy compared to controls.
 - Measured from time of disease onset to time of intubation.
- To estimate the **time to improvement in oxygenation** in patients treated with anti-IL-8 therapy compared to controls.
 - Measured as time from start of treatment until $\geq 30\%$ decrease in oxygen requirement compared to baseline
- To measure the **proportion of patients requiring ICU admission at 1 month** in patients treated with anti-IL-8 therapy compared to controls.
 - Measured as the number of patients requiring ICU admission over their hospitalization over the number of evaluable patients.
- To assess the **safety and tolerability** defined as adverse events graded by CTCAE v5.0 in patients treated with anti-IL-8 therapy compared to controls.
- To assess the **duration of hospitalization** in patients treated with anti-IL-8 therapy compared to controls.
 - Measured as time from admission to time of discharge.
- To compare the raw 7-point ordinal scale scores at day 14 in patients treated with anti-IL-8 therapy versus controls.

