7.5 Randomization and Blinding

Patients will be randomized 2:1 (anti-IL8: standard of care) in “real-time”. If the subject’s eligibility status is confirmed, the statistician will send the randomization assignment based on the pre-generated randomization scheme.

This is an open-label study.

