11.2.11 Proportion of patients with multiorgan failure at 1 month

The proportion of patients with multiorgan failure will be defined as the number of patients with multiorgan failure during their hospitalization measured at 1 month over the number of evaluable patients.

11.2.12 Time to improvement in NEWS2 score ≤ 2

Determine the time to improvement in NEWS score will be defined as time from start of treatment until NEWS score ≤ 2 and maintained for at least 24hrs. The NEWS 2 score is calculated based respiratory rate, oxygen saturation, systolic blood pressure, pulse rate, level of consciousness/confusion and temperature.

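### Score 7 has no discharge-destination rule and a single day's score is enough, so a hospice discharge or a self-discharge on oxygen counts as primary improvement

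*Combined protocol and SAP*

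**What the plan says.** The primary objective in Section 2 is "Measured from baseline to 2 point or greater improvement in 7-point ordinal scale". Section 11.1.1 counts days "required from the start of treatment to the improvement of clinical status (2 points) assessment from baseline based on the 7-point ordinal scale", and censors patients who have no event. Neither place asks for a second score or a minimum duration.

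The upper scores are set out in Section 11.1.1 and repeated in footnote l of the Section 10 calendar. Score 5 is a hospitalized patient "not requiring supplemental oxygenation and requiring ongoing medical care (COVID-19 related or otherwise"; score 6 is likewise in hospital and off oxygen, and the list ends "no longer requires ongoing medical care, (7) not hospitalized". Score 7 carries no condition on destination, oxygen use at departure, or what happens next.

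Two other endpoints do carry a persistence rule. The oxygenation gain in Section 11.2.4 must be "sustained for at least 48hrs or until discharge", and the NEWS2 target in Section 11.2.12 must be "maintained for at least 24hrs".

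Section 7.5 states: "This is an open-label study". No blinded or independent rater of the scale is named. The calendar schedules the scale at screening and daily in hospital, with no entry in the follow-up column.

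**The concern.** A time-to-improvement endpoint should count patients who got better. Here the best score is given for being out of hospital, whatever the reason. A score-4 patient who dies on the ward has no event and is censored; the same patient sent to hospice the day before has a 3-point gain and is a success. The place of death would then decide the primary outcome. Likewise, a ventilated patient (score 2) who is on supplemental oxygen alone for one daily score (score 4), and is then re-intubated or dies, is already a success, and no rule reverses it.

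Exits of equal frequency in both arms pull the hazard ratio toward 1 and cost power. If the timing of discharge or the scoring differs by arm, which an open-label design allows, the comparison is biased.

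**Working it through.** **Which scores make an event.** Eligibility (Section 5.1) admits baseline scores of about 2 to 5. A gain of at least 2 points needs:

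| Baseline | Scores that count as an event |
|---|---|
| 2 | 4, 5, 6, 7 |
| 3 | 5, 6, 7 |
| 4 | 6, 7 |
| 5 | 7 |

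Leaving hospital is an event at every baseline score and the only route at baseline 5. The step from 5 to 6 decides an event only at baseline 4.

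**The plan's own figure.** Section 13.4 gives 41 events for a hazard ratio of 0.40, 2:1 allocation, one-sided alpha 0.025 and 80% power. The Schoenfeld formula gives (1.96 + 0.8416)² / [(2/9)(ln 0.40)²] = 42.07, or 43 when rounded up. Power at 41 events is Φ(√(41 × 2/9) × 0.9163 − 1.96) = Φ(0.806) = 0.79. The plan's figure is reproduced closely enough to build on.

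**Inputs for the size.**
- Medians from the Synopsis: 5 days control, 2 days drug. Section 13.1 has the two arms the other way round; that is a separate matter, and the Synopsis direction is used because it is the one in which the drug helps.
- Daily hazards under the plan's exponential assumption: ln 2/5 = 0.1386 control, ln 2/2 = 0.3466 drug. Their ratio is 2.50, the inverse of the plan's 0.40.
- Daily rate h of exits without recovery: **assumed** 0.01 to 0.02, equal in both arms. The documents give no figure.

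**Results.** The share of events that are exits is h/(λ + h), where λ is the arm's daily hazard. The observed hazard ratio is (0.3466 + h)/(0.1386 + h).

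| | h = 0.01 | h = 0.02 |
|---|---|---|
| Control share | 0.01/0.1486 = 6.7% | 0.02/0.1586 = 12.6% |
| Drug share | 0.01/0.3566 = 2.8% | 0.02/0.3666 = 5.5% |
| Hazard ratio for improvement | 2.40 | 2.31 |
| Power at 41 events | Φ(3.018 × 0.875 − 1.96) = 0.75 | Φ(3.018 × 0.838 − 1.96) = 0.72 |

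If the 41 events split 2:1 (13.7 control, 27.3 drug), the expected exits are 13.7 × 0.067 + 27.3 × 0.028 = 1.7 at the low end and 13.7 × 0.126 + 27.3 × 0.055 = 3.2 at the high end.

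**If the arms differ.** Suppose the drug has no effect, but drug-arm patients are scored up or discharged at a rate higher by 5, 10 or 20% (again assumed). The one-sided false-positive rate at 41 events is Φ(3.018 × ln r − 1.96), with r = 1.05, 1.10 or 1.20: 0.035, 0.047 or 0.079, against 0.025 nominal. A difference the other way would make the test conservative.

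**The case against.** Several objections have force.

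- **Transfer.** A reader might infer that moving to another acute hospital earns score 7. The text does not support that. Scores 2 to 6 refer to a hospitalized patient, not to one at this centre, so a transferred patient is not plainly score 7. What is missing is a rule for scoring that patient.
- **Score 6.** A reader might also infer that one unblinded opinion turns a non-recovery into an event. Score 6 also requires being off supplemental oxygen, and the judgement is decisive only at baseline 4. Someone off oxygen and thought to need no further care has improved on any ordinary reading. This is a question of subjective rating, not of counting non-recoveries.
- **Persistence.** The oxygenation endpoint accepts discharge in place of 48 hours, so it too ignores destination. A first-passage definition contradicts nothing in the plan, and relapse or death would still show in time to death, 1-month mortality and the day-14 score. Those are secondary endpoints and leave the primary definition as it is.
- **Frequency.** The exit rate is assumed. Section 5.2 excludes patients with an expected non-COVID survival under 2 months and those with multi-organ failure needing vasopressors, CVVH or ECMO, which should make hospice discharge rarer. Against that, Section 3.1 cites a mortality of about 20–25% in severe disease, and Section 13.3 expects cancer patients in the trial.

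These narrow the point without removing it. On the plain wording, hospice discharge, self-discharge on oxygen and a one-day gain all count.

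**Conclusion.** The point holds in this form: the stated rule, applied exactly, classes some patients who have not recovered as primary improvements. The cause is the missing destination condition on score 7 and the acceptance of a single daily score.

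Under the assumed 1–2% per day, equal in both arms and exponential, the effect is modest: about 2–3 of 41 events, a hazard ratio of 2.40–2.31 instead of 2.50, and power of 0.75–0.72 instead of 0.79. That dilution works against the drug.

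A reader might go further and infer that the definition favours the drug. The documents do not support that. They show that unblinded discharge and scoring could differ by arm, but give neither the size nor the direction. The change is worth making because it is cheap now and open to dispute once outcomes are known.

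**What to change.** In Section 11.1.1 and calendar footnote l, state that:

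1. Score 7 counts as an event only for live discharge not to hospice. A hospice discharge is not an improvement.
2. A self-discharged or transferred patient is scored on the last charted oxygen and care status. A patient in another acute hospital remains hospitalized for scoring.
3. Scores 2 to 5 are derived from the charted oxygen device.

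Rule 2 avoids coding every self-discharge as a failure, which would misclassify patients who leave after recovering.

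Add a sensitivity analysis of the primary endpoint in which the 2-point gain must appear on two consecutive daily scores, or end in a qualifying discharge, and in which exits without recovery are not events.

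The cost is one discharge-destination field on the case report form; the daily scores and oxygen data are already collected. A few events will be lost, including a baseline-5 patient who self-discharges at status 6, a gain of only 1. In the sensitivity analysis, some events will fall about a day later.
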